#### *Exclusion criteria*

- Patients refusal to participate in the study
- unable to give informed consent
- chronically bedridden before inclusion
- clinical frailty scale  $\geq 7$  (42)
- chronic ventilation (more than 24 hours) before admission to the intensive care unit
- Elevated intracranial pressure / risk for elevated intracranial pressure / recent cerebral hemorrhage
- Pregnancy
- Pre-existing neuromuscular disease resulting in chronic limitation of strength and performance
- Sternotomy / Sternectomy during a surgical procedure

Patients meeting the following criteria will be retrospectively selected for the historical comparison group:

- planned surgical procedure
- Postoperative intensive care and therapeutic treatment
- Duration of ventilation > 48 hours
- age  $\geq 18$  years
- Weight >45 kg and <135 kg
- Body height >1.50 m and <1.95 m
- Patients who met any of the exclusion criteria during their intensive care unit stay will not be included in the historical group.

No matching is planned.

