#### 7.4. TERMINATION CRITERIA FOR PATIENTS

All patients included in the study are free to withdraw their consent to participate in the study, in whole or in part, at any time and without giving reasons. In such a case, patients will be asked to state the reason for withdrawal but will be informed that they are not required to do so. Time and reasons for withdrawal (if given) will be documented. Patients can be excluded from the study if a violation of inclusion or exclusion criteria is subsequently determined or if the data collection is incomplete.

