## 8. METHOD AND PROCEDURE

Patients of the LMU Hospital will be included according to the inclusion and exclusion criteria (see 5.2. and 5.3.). All patients who are to be treated surgically and whose postoperative care is planned in the anesthesiological intensive care units will be screened according to the inclusion and exclusion criteria. If the expected duration of postoperative ventilation exceeds 48 hours and there are no contraindications, the patient is given an information session. This should be done preoperatively with awake patients who are able of giving consent. In case of consent, the patient will be included in the study.

In addition, within the scope of the experience of the mobilizing specialists, nurses, physiotherapists, and physicians will be included according to inclusion and exclusion criteria, who are predominantly assigned to the intensive care units of the LMU Hospital and from T2 onwards to the anesthesiological intensive care units.

With the start of robot-assisted early mobilization, the survey will be conducted within the framework of organizational feasibility. This is carried out by project staff and ward staff. The survey ends with the last robot-assisted mobilization.

[figure not shown]

Fig. 5: Detailed procedure of the study with examination times of the patients

All patients will receive a physical examination at different time points to assess physical functionality and muscle strength, as well as a sonographic examination of leg muscles, diaphragm, and lungs. These examinations should be performed on day -1 (preoperatively), on postoperative days 1,2,3, then once a week if the patient remains in the Intensive Care Unit, on day 28, on the day of discharge from the Intensive Care Unit, and on a follow-up examination approximately 3 months after discharge from the Intensive Care Unit. The follow-up examination should only take place if the patients present themselves at the LMU Hospital anyway due to medically indicated follow-up examinations (not study-related). Alternatively, patients can be asked about their condition by telephone (see Fig. 5).

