#### Conventional early mobilization

The comparison group is a historical collective, which also meets the inclusion and exclusion criteria of the study. These patients were early mobilized following the ward routine of the intensive care units conventional early mobilization according to the instructions of the treatment team, consisting of physicians, nurses, and physiotherapists. Conventional early mobilization cannot be precisely defined on the basis of a retrospective study (45, 15). The information used for the study regarding early mobilization and the defined outcome criteria of the patients is taken from the routinely collected data.

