### *Individual measures during study procedure*

### *Education and Informed consent*

Only patients who are capable of giving consent and can be informed preoperatively will be included. Informed consent will be obtained from all patients who meet the other inclusion criteria. If the patients withdraw their consent to the study at a later point in time, they will be asked whether the data collected up to this point in time may still be used. Otherwise, all data collected up to that point will be destroyed. There is no intention to include persons from the group of persons in need of special protection.

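### Historical controls are excluded for criteria met at any time in the ICU, whereas robot patients' eligibility is set before surgery, so controls are selected on post-baseline events

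*Protocol*

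**What the plan says.** Section 7.2 lists nine exclusion criteria for patients and then describes how the historical group is chosen. The last bullet of that description reads "Patients who met any of the exclusion criteria during their intensive care unit stay will not be included in the historical group". It is mandatory and its window is the ICU stay. The same section rules out matching.

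For robot patients the time point is before surgery. Section 8 says of the information session: "This should be done preoperatively with awake patients who are able of giving consent"; a patient who consents is then included. The consent paragraph in section 8.3 repeats the condition: "Only patients who are capable of giving consent and can be informed preoperatively will be included".

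Section 7.4 contains the only provision for removing an enrolled patient other than at the patient's own wish: "Patients can be excluded from the study if a violation of inclusion or exclusion criteria is subsequently determined or if the data collection is incomplete".

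Section 8, on conventional early mobilization, describes the controls as follows: "The comparison group is a historical collective, which also meets the inclusion and exclusion criteria of the study". It does not mention that the criteria are applied over a different period.

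**The concern.** The patient-outcome questions rest on one contrast, robot patients against historical controls. It is fair only if both groups are defined by what was known at the same point in the course. Here the control group is defined partly by what happened after that point, in the period in which ventilation time, muscle loss and length of stay accrue.

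Some listed conditions can appear for the first time in the ICU. The clearest is "Elevated intracranial pressure / risk for elevated intracranial pressure / recent cerebral hemorrhage". A control who develops it must be left out. A robot patient who develops it has already been included, and nothing requires removal. If such patients have worse courses, the control group loses some of its worst results through a rule that does not bind the robot group equally.

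**Working it through.** No figure in the protocol underlies this point, so the check is a comparison of the text followed by an illustration of size.

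**The two windows side by side**

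- Controls (7.2): criteria applied in retrospect over the ICU stay; exclusion mandatory.
- Robot patients (8 and 8.3): criteria applied at preoperative screening and consent.
- Robot patients after inclusion (7.4): exclusion possible but optional, for a criteria violation found later or for incomplete data. A violation found later most naturally means an eligibility error at entry, though the text does not say so.
- Other provisions: section 8 ends a robot patient's study period at the three-month follow-up, at the close of recording, or at death. Section 8.3 allows a mobilization session to be withheld or stopped, which does not take the patient out of the study.

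**Which of the nine criteria can newly arise in the ICU**

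- Fixed earlier by their wording: chronically bedridden, chronic ventilation, neuromuscular disease.
- In practice baseline states: frailty score, pregnancy.
- Not applicable to controls, who were never approached: refusal.
- Can newly arise: the intracranial item, and a sternotomy at a later operation.
- Unclear as worded: "unable to give informed consent", discussed under the objection.

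**Size, by assumption**

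Let q be the share of otherwise eligible controls dropped by the rule, and d the amount, in SD of an outcome, by which they are worse than those kept. Suppose there is no treatment effect and every such robot patient is retained. With m the mean of patients without the event:

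- robot mean = (1 - q) × m + q × (m + d) = m + q × d
- control mean = m
- spurious difference = q × d, against the robot

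Results:

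- q = 0.03, d = 1: 0.03 × 1 = 0.03 SD
- q = 0.05, d = 1.5: 0.05 × 1.5 = 0.075 SD
- q = 0.10, d = 2: 0.10 × 2 = 0.20 SD

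Of every 30 otherwise eligible controls, 0.03 × 30 = 0.9 to 0.10 × 30 = 3 would be passed over. Any use of section 7.4 to remove the corresponding robot patients shrinks the difference, to zero if all of them were removed.

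For scale, with 30 per group (the executive summary's approximate figure) the standard error of a mean difference is √(1/30 + 1/30) = 0.26 SD. The upper end of the range is below one standard error.

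**The opposing asymmetry**

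Section 7.2 requires controls to have been ventilated for more than 48 hours, but robot patients only to be expected to be. Short courses are thus removed from the controls and can remain among robot patients. On ventilation time this favours the robot.

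**The case against.** The strongest reply is that the wording is loose but the effect is small and not one-sided. Most of this stands, and it rules out four stronger readings that a reader might infer.

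- *That such patients are removed from the control group only.* Section 7.4 permits later exclusion of robot patients, and its incomplete-data clause could also take out complicated courses, since the function and ultrasound outcomes need repeated bedside examination. Nor can sternotomy be fully settled before the operation, so an unplanned one in a robot patient could only be dealt with afterwards. What survives is the difference between a mandatory rule and a discretionary one.
- *That complicated courses in general are removed.* Sepsis, organ failure, reoperation without sternotomy and death are not exclusion criteria. The rule reaches essentially one item plus a rare second.
- *That the consent criterion empties the control group.* Read literally, anyone sedated and ventilated for over 48 hours was unable to consent at some time. But controls come from routine data, and their list omits the consent item, so this cannot be the intended meaning. It calls for clarification and is not a measure of size.
- *That the whole comparison is biased against the robot.* The ventilation criterion pushes the other way on ventilation time, and the documents do not allow the two to be weighed.

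The reply does not remove the core point. The protocol does not leave the control window open; it fixes it on the ICU stay. Two opposing biases of unknown size cannot be relied on to cancel.

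**Conclusion.** The point holds in limited form. The control rule in 7.2 selects on post-baseline events, and no equally binding rule applies to robot patients. Section 8 describes the two groups as meeting the same criteria without noting the difference in timing.

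Taken alone, the rule works against the robot, provided that patients with the listed events do worse. The illustrative 0.03-0.20 SD rests wholly on assumed values (3-10% removed, 1-2 SD worse, no corresponding robot patients removed); the protocol supplies none of them. The net direction of the comparison is undetermined. This is worth correcting because it is systematic and cheap to avoid, but it is not a defect on which the study stands or falls. Confidence is medium, mainly because the practical use of section 7.4 is unknown.

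**What to change.** Four changes of wording:

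1. Section 7.2, last control bullet: apply the exclusion criteria to controls on their status as documented before the index operation. For the sternotomy criterion, the index operation itself counts, in both groups.
2. Section 7.2: state that the refusal and consent-capacity criteria do not refer to events in the ICU. Refusal is not applicable to controls, and capacity means the preoperative state.
3. Sections 7.2 and 7.4: state that a criterion first arising during the ICU stay does not remove a patient from the analysis in either group and is reported as a complication. Changing 7.2 alone would leave it in conflict with 7.4.
4. Section 8, conventional early mobilization: bring the description of the comparison group into line with the revised 7.2 and 7.4.

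The cost is small. The preoperative status comes from the same electronic record, and no prospective procedure changes. A few more complicated controls enter, so the control variance rises slightly. The protocol's own rule on amendments requires consultation with the ethics committee. The expected-versus-observed ventilation criterion is not cured by these changes and needs separate attention; once this rule is aligned, it would remain as an asymmetry in the robot's favour on ventilation time.

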### 7.3. NUMBER OF PATIENTS

In order to test correlations using multiple-variate models (multiple linear regressions) with a statistical power of 80% on approximately 8 independent variables (UV) compared to the dependent variable (AV), an approximate total sample size of 50 subjects is required.

Thus, with an expected drop-out of 10%, 55 patients (robotic intervention and historical comparison group) should be included in the study. A sample size of 20 subjects is considered a lower limit with moderately strong associations between UVs and AV and inclusion of a maximum of 5 UVs, with  $\alpha=5\%$  and  $\text{power}=80\%$  (43, 44). In this regard, if 30-35 patients are included in the robot-assisted intervention and a maximum of 6 UVs, meaningful results can be expected to be obtained in a manageable period of time.

All patients will be included in the intervention only if written informed consent is obtained. Due to the expected patients' recruitment (6-8 patients/month) with a given number of cases (30-35 patients in the intervention), the study is expected to last five to six months from the start. The recruitment rate depends on the number of patients.

In general, all patients meeting the above-mentioned criteria will be included in the study. The study is completed as soon as the required number of patients has been recruited for the intervention. The corresponding number of cases for the historical group will be taken from the routine data.

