## 4.3 EVALUATION OF THE EFFECTS ON PATIENT OUTCOMES

- Can robot-assisted early mobilization improve muscle strength and reduce muscle loss compared with the historical collective?
- Can robot-assisted early mobilization reduce the duration of ventilation?  
In addition, further questions will be addressed:
- Does robotic-assisted early mobilization result in changes in consciousness, pain, cognition, health perception, cardiocirculatory and respiratory function, other factors such as pressure ulcers, bowel emptying, insulin requirements, and duration of treatment?

For this purpose, the following outcome criteria of the patients are examined.

Primary outcome criteria	Physical function/muscle strength	Surveyed according to the MRC (Medical Research Council) classification on upper and lower extremity and using the FSS-ICU (32, 33) at discharge ICU.
	Parameters for the assessment of muscle deterioration	Muscle thickness of quadriceps femoris muscle (thickness quadriceps femoris muscle and cross sectional area rectus femoris muscle)  Muscle thickness of the diaphragm / Thickening fraction diaphragm  Diaphragm mobility at discharge ICU
	Ventilation time	Duration (d) of invasive ventilation

Secondary outcome criteria	Consciousness/ cognition/ pain/ health perception	Pain using the Visual Analog Scale (VAS) (before and after mobilization).  Delirium incidence using the CAM ICU (34): number of days without delirium.  Sedation level using the Richmond Agitation Sedation Scale (RASS)(35)  level of consciousness using the Glasgow Coma Scale (GCS) (36)  Health-related quality of life after 3 months using the SF-36 questionnaire (37)
	Hemodynamics	Blood pressure / catecholamine demand / heart rate / cardiac output / oxygen consumption
	Respiration	CPAx-respiratory function(38) / oxygenation index / lung ultrasound parameter
	Others	Intestinal evacuation (yes/no)  Decubitus (grade classification 1-4 according to Shea (39))  Lactate level before and after mobilization (if laboratory value available)  Insulin requirement
	ICU Scores	SOFA [39] / Apache II (40) / SAPS II (41)  Intensive care unit treatment duration / inpatient treatment duration

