## 9. BIOMETRY

In the context of organizational feasibility, descriptive data is reported and visualized for robot-assisted VEM. Subsequently, regression analyses are used to contextualize and quantify the data. Depending on the variables and the type of distribution, they are quantified after calculating degrees of freedom and correlations are tested using applicable analysis methods.

Descriptive data on stress experience and physical behavior will be collected within a robot-assisted mobilization situation and analyzed and visualized using descriptive statistics.

Within the study population, conventional early mobilization of critically ill intensive care patients (historical comparison group) will be compared with robot-assisted early mobilization. The data will be evaluated by graphical representations of the individual parameters in the course by means of box plots and scatter diagrams. Associations between parameters are quantified using appropriate (depending on scale level and distribution) correlation coefficients. For comparison between conventional and robot-assisted VEM, commonly used robust statistical methods are applied.

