From the data obtained, improved therapy concepts can be developed and the use of robot-assisted mobilization can be established as part of a new standard of care. This study makes a significant contribution to a future improvement of therapy for critically ill patients. If the measures of robot-assisted VEM prove to be superior to the measures of historical, conventional VEM, the new treatment technique could be quickly implemented in the clinical routine of intensive care units on the basis of the project presented here.

The data collected during the study are not available to the treating physicians during the patient recruitment phase. This way, in particular, no negative influence on the therapy of the individual patient can arise. Even if conclusions regarding the treatment of future patients or patients from other intensive care units cannot be drawn from the data obtained in an unlimited and uncritical manner, the study presented here provides a valuable gain in knowledge with the aim of comparatively examining different forms of early mobilization of the effect on a specific patients population. By simultaneously surveying the experience and behavior of the mobilizing professionals, it is also possible to record their workload when using the new therapy. Given the high workload in intensive care units, a feasibility study is essential, so the focus of this study is on users, patients, and structures.

In summary, this study makes an important and necessary contribution to improving the therapy of critically ill patients. There are no study-related burdens for the individual patients and participation in the study is without risks for the patients.

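### The 80% power in section 7.3 refers to correlations with unnamed variables and cannot be read as power for the robot-versus-historical comparison

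*Protocol*

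**What the plan says.** The patient-outcome questions in section 4.3 are about the robot. One reads "Can robot-assisted early mobilization reduce the duration of ventilation"; the other asks the same of muscle strength and muscle loss against the historical collective. Section 6 repeats the comparison as a design aim. Section 10 looks ahead to its use in routine care: "If the measures of robot-assisted VEM prove to be superior to the measures of historical, conventional VEM".

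The sample size in section 7.3 rests on something else. Its starting point is "In order to test correlations using multiple-variate models (multiple linear regressions) with a statistical power of 80% on approximately 8 independent variables (UV"), from which "an approximate total sample size of 50 subjects is required". Then, "with an expected drop-out of 10%, 55 patients (robotic intervention and historical comparison group) should be included in the study". The section adds a lower limit of 20 subjects with at most 5 independent variables. That is the only sentence that states α = 5%, and it describes the effect only in words, as moderately strong. It closes with a third variant: "if 30-35 patients are included in the robot-assisted intervention and a maximum of 6 UVs, meaningful results can be expected".

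None of these variables is named. Group is not identified as one of them, and no group difference or SD is given.

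Section 9 does announce a comparison of conventional with robot-assisted mobilization, by robust methods that it does not name. It attaches no alpha, power or covariate adjustment to that comparison. It mentions regression only in its paragraph on organizational feasibility, which is also where "correlations are tested using applicable analysis methods" stands. Section 7.2 says that the historical group will not be matched.

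**The concern.** A reader of section 7.3 will take the 80% as the trial's power for its patient-outcome question, but the text does not support that. A regression with about eight predictors can be tested as a whole or one coefficient at a time. Only a test of the group coefficient speaks to the robot. A whole-model test can be significant because age or illness severity predicts ventilation time, whether or not the robot does anything.

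Two things are at stake. The number of patients has no stated link to the comparison that section 10 would use to support wider adoption. And that comparison has no planned adjustment, although the groups are neither randomized nor matched, while the predictors that could serve for adjustment appear only in the sample-size section.

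**Working it through.** **Inputs.** From section 7.3: N = 50 with about 8 independent variables (k = 8) and 80% power; 10% drop-out and 55 in total; N = 20 with k = 5, α = 5% and 80% power. From section 1: about 30 robot and 30 historical patients. *Assumed:* α = 5% for the 8-variable model, since the text gives it only for the 20-subject case, and every effect size, since the protocol gives no number.

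**Formulas.** With noncentrality λ = f²·N, power is the probability that a noncentral F exceeds its 5% critical value. The degrees of freedom are (k, N−k−1) for the whole model and (1, N−k−1) for one coefficient, two-sided. R² = f²/(1+f²).

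**1. Reproducing 50 and 55.** Drop-out: 50/0.9 = 55.6, or 50 × 1.1 = 55; the difference of one patient does not matter. The 50 itself cannot be derived without an effect size. N needed for 80% power with k = 8:

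| f² assumed | Whole model | One coefficient, two-sided |
|---|---|---|
| 0.15 | 109 | 55 |
| 0.25 | 69 | 34 |
| 0.35 | 52 | 26 |

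Two readings come close to the stated figures:
- **Whole-model test.** At N = 50, df = (8, 41), 80% power needs f² = 0.36, so R² = 0.36/1.36 = 0.265.
- **One coefficient.** At f² = 0.15, λ = 0.15 × 50 = 7.5 gives 76% at N = 50, and λ = 0.15 × 55 = 8.25 gives 80% at N = 55.

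**2. Does the lower limit settle it?** For N = 20 and k = 5, the whole-model test needs f² = 0.94 (R² = 0.48). One two-sided coefficient needs f² = 0.45 (partial r = 0.56). One one-sided coefficient at f² = 0.35 has 81% power. The section states neither sidedness nor effect size, so the reading stays open.

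**3. What a significant whole-model test says about the robot.** Simulation, 20,000 runs: N = 50 (25 + 25), robot coefficient zero, seven other independent predictors together carrying f² = 0.36. The whole-model test is significant in 77% of runs and the robot coefficient in 5%. Another simulation of 6,000 runs gave 78% and 5%.

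**4. What these numbers can detect for the group contrast.** Two-sample t test, two-sided 5%, unadjusted, noncentrality d·√(n₁n₂/(n₁+n₂)), d in SD units:

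| Robot + historical | Difference at 80% power | Power at 0.5 SD | Power at 0.8 SD |
|---|---|---|---|
| 25 + 25 | 0.81 SD | 41% | 79% |
| 30 + 25 | 0.77 SD | 44% | 83% |
| 30 + 30 | 0.74 SD | 48% | 86% |

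Cross-check: for equal groups and a group term uncorrelated with the other predictors, f² = d²/4. So f² = 0.15 corresponds to d = 2√0.15 = 0.77 residual SD, in line with the table. If the author meant one coefficient and that coefficient was group, the sentence would be a power statement for a difference of roughly 0.8 SD. The section says neither.

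**The case against.** The case for leaving the text alone has real parts.

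- *Section 9 does plan the group comparison.* This stands: the comparison is not missing. But it carries no alpha, power or adjustment, so the stated power is not attached to it.
- *The 80% may already belong to one coefficient.* This stands as a possibility; step 1 shows that the numbers fit. Even so, no coefficient is named.
- *Model details belong in the statistical analysis plan.* True of the exact model and covariates. It does not cover the basis of the sample size, which the protocol fixes itself and fixes on a hypothesis other than its objective.
- *Feasibility comes first, and section 10 is cautious about generalizing.* True, and it limits the severity. The effects on patient outcomes still have their own primary criteria.

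Several stronger readings are tempting, and the protocol does not support them:

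- *That testing 5, 6 or 8 predictors at 5% each gives a 23%, 26% or 34% risk of a false robot claim.* Those figures (1 − 0.95^k, independence assumed) are the chance that any predictor is falsely significant. The robot coefficient itself stays at about 5%. Moreover, α = 5% is stated only for the 20-subject, 5-variable case.
- *That the robot term really has 31% power.* This needs the back-solved f² of 0.36 split evenly over eight variables. At N = 50, the robot term's power is 99% if it carries all of that f², 83% for half, 67% for a third and 54% for a quarter. The protocol supports no particular share.
- *That the variant with 30-35 patients excludes the group contrast.* It would if fitted in robot patients alone. But section 7.3 defines the 55 as both groups together and takes the historical cases from routine data, so a pooled reading is more natural.
- *That the sentence on testing correlations in section 9 governs patient outcomes.* It stands in the feasibility paragraph.

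**Conclusion.** The point holds as a mismatch between the basis of the sample size and the objective. The 80% cannot be read as power for robot versus historical, because section 7.3 does not say which test or which effect it refers to, and the candidate readings differ in substance: R² of about 0.27 for a whole model, or f² of about 0.15 for one coefficient. Under the first, significance is compatible with no robot effect in about 78% of trials, on the assumption that other variables carry the whole association.

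The planned numbers are not useless for the group contrast. Unadjusted and under normality, they detect about 0.74 to 0.81 SD at 80% power, with 41% to 48% power for 0.5 SD. Whether a difference of that size is plausible cannot be judged from the protocol. The change should be made; it does not put the conduct of the study in question.

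**What to change.** In sections 7.3 and 9:

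1. For each patient outcome available in both groups, make the robot-versus-historical indicator, in a regression on the pooled groups, the tested term at two-sided 5%. The restriction matters: historical data come from routine records, while section 8.3 lists the ultrasound and functional examinations as study-related, so historical values may not exist for some primary outcomes.
2. Treat the other independent variables as adjustment variables, reported as estimates with confidence intervals. Age and the severity scores are already on the data list in section 8.3.
3. Label correlation analyses, and any model fitted in robot patients only, as exploratory.
4. Restate the power sentence for the group term with its assumed effect, for example 80% power for about 0.81 SD (25 + 25) to 0.74 SD (30 + 30), unadjusted and two-sided 5%. Otherwise delete it.

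The cost is a few sentences, with no new patients or measurements. The general 80% claim is lost, and associations with other variables can be reported only as exploratory.
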